7.2 Participant Discontinuation/Withdrawal from the Study

- A participant may withdraw from the study at any time at his/her own request, or may be withdrawn at any time at the discretion of the investigator for safety, behavioral, compliance, or administrative reasons. This is expected to be uncommon.
- The reason for withdrawal should be clearly documented in the source documents and in the CRF: Adverse Event, Lost to Follow-up, Protocol Deviation, or Withdrawal by participant.
- The participant will be permanently discontinued both from the study intervention and from the study at that time.
- If the participant withdraws consent for disclosure of future information, the Sponsor may retain and continue to use any data collected before such a withdrawal of consent.
- If a participant withdraws consent, he/she may request destruction of any samples taken and not tested, and the investigator must document this in the site study records.
- Withdrawn participants will not be replaced.

Follow-up of Discontinuations

For participants who have prematurely terminated the study, the site should attempt to contact them and complete all scheduled safety follow-ups, except if they specified that they do not want to be contacted again and it is documented in the source document.

For participants where the reason for early termination is lost to follow-up, the site will not attempt to obtain further safety information. See [Section 7.3](#) for definition of “lost to follow-up”.

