2.3.4 Overall Benefit-Risk Conclusion

Considering the measures taken to minimize risk to participants enrolled in this study, the potential risks that may result from study participation are balanced by the anticipated benefits that may be afforded to participants.

3 Objectives and Endpoints

Table 3.1: Objectives and endpoints

Objectives	Endpoints

Immunogenicity
 
To assess the immune response of the 3 SP0202 formulations, Prevnar 13, and Pneumovax 23, 30 days after the administration of the single dose vaccination
	
• Serotype-specific OPA titers for all pneumococcal serotypes included in the SP0202 formulations, as determined by multiplex opsonophagocytic assay (MOPA), at baseline (D01) and 30 days after vaccination (D31)• Serotype-specific OPA titers ratio (post/pre-injection) for all pneumococcal serotypes included in the SP0202 formulations as determined by MOPA• Serotype-specific IgG concentrations for all pneumococcal serotypes included in the SP0202 formulations as measured by electro-chemiluminescence assay (ECL), at baseline (D01) and 30 days after vaccination (D31)• Serotype-specific IgG concentration ratios (post/pre-injection) for all pneumococcal serotypes included in the SP0202 formulations as measured by ECL

Safety
 
To assess the safety profile of the 3 SP0202 formulations, Prevnar 13, and Pneumovax 23
	
• Presence of any unsolicited systemic AEs reported in the 30 minutes after injection of a SP0202 formulation, Prevnar 13, or Pneumovax 23• Presence of solicited (ie, pre-listed in the participant's DC and in the CRF) injection site reactions occurring up to 7 days after the day of injection (D08) of a SP0202 formulation, Prevnar 13, or Pneumovax 23• Presence of solicited (ie, pre-listed in the participant's DC and in the CRF) systemic reactions occurring up to 7 days after the day of injection (D08) of a SP0202 formulation, Prevnar 13, or Pneumovax 23• Presence of unsolicited (spontaneously reported) AEs up to 30 days after the day of injection (D31) of a SP0202 formulation, Prevnar 13, or Pneumovax 23• Presence of SAEs and AESIs, throughout the study period (up to 6-month follow-up)

4 Study Design

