7.3 Lost to Follow-up

A participant will be considered lost to follow-up if he or she repeatedly fails to return for scheduled visits and is unable to be contacted by the study site.

The following actions must be taken if a participant fails to return to the site for a required study visit or cannot be contacted as planned in the SoA:

- The site must attempt to contact the participant and reschedule the missed visit as soon as possible and counsel the participant on the importance of maintaining the assigned visit schedule and ascertain whether or not the participant wishes to and/or should continue in the study.
- Before a participant is deemed lost to follow-up, the investigator or designee must make every effort to regain contact with the participant (where possible, 3 telephone calls and, if necessary, a certified letter to the participant's last known mailing address or local equivalent methods), or at least to determine his/her health status while fully respecting his/her rights. These contact attempts should be documented in the participant's medical record.
- Should the participant continue to be unreachable, he/she will be considered to have withdrawn from the study.

Discontinuation of specific sites or of the study as a whole are handled as part of [Appendix 10.1](#).

8 Study Assessments and Procedures

- Study procedures and their timing are summarized in the SoA. Protocol waivers or exemptions are not allowed.
- Immediate safety concerns should be discussed with the Sponsor immediately upon occurrence or awareness to determine if the participant should continue or discontinue study intervention.
- Adherence to the study design requirements, including those specified in the SoA, is essential and required for study conduct.
- All screening evaluations must be completed and reviewed to confirm that potential participants meet all eligibility criteria. The investigator will maintain a screening log to record details of all participants screened and to confirm eligibility or record reasons for screening failure, as applicable.

Blood samples will be collected as described in the SoA table ([Section 1.3](#)).

The maximum amount of blood collected from each participant over the duration of the study, including any extra assessments that may be required, will not exceed 40 mL. Repeat or unscheduled samples may be taken for safety reasons or for technical issues with the samples.

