4.3.1.2.5 SAEs

An event will be considered as a serious event if “Yes” is checked for “Serious” in the CRF.

SAEs will be analyzed throughout the study using at least the following periods:

- Within 30 days after the injection
- During the 6-month follow-up period (ie, from 31 days [from D32] after injection until the last participant contact)
- During the study (ie, all SAEs occurred during the study)

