5.3 Population for Analyses

Population	Description
Randomized	All participants with data in the CRF
Safety Analysis Set (SafAS)	Participants who have received the study vaccine. All participants will have their safety analyzed according to the vaccine they actually received. Safety data recorded for a vaccine received out of the protocol design will be excluded from the analysis (and listed separately).
Full analysis set (FAS)	Subset of randomized participants who received at least 1 dose of the study vaccine and had a valid post-vaccination blood sample result (serotype specific IgG concentration or serotype specific OPA titer for at least one serotype). Participants will be analyzed according to the intervention to which they were randomized.
Per-protocol analysis set (PPAS)	
Subset of the FAS. Participants presenting with at least one of the following relevant protocol deviations will be excluded from the PPAS:
 
 • Participant did not meet all protocol-specified inclusion criteria or met at least one of the protocol-specified exclusion criteria • Participant did not receive vaccine • Participant received a vaccine other than the one that he / she was randomized to receive • Preparation and / or administration of vaccine was not done as per-protocol • Participant did not provide the post-dose serology sample at V02 in the proper time window or a post-dose serology sample was not drawn • Participant received a protocol-prohibited therapy / medication / vaccine 
In addition to the reasons listed above, participants will also be excluded from the PPAS if their Visit 02 / post-vaccination serology sample did not produce a valid test result (ie, results for all pneumococcal serotypes for both OPA and IgG are missing).
 
In the event of a local or national immunization program with a pandemic influenza vaccine, participants who receive 1 or more doses of a pandemic influenza vaccine at any time during the study will not be withdrawn from the study.
 
As the COVID-19 vaccination campaign has been deployed during the study period, participants who receive 1 or more doses of COVID-19 vaccine during the study period will not be withdrawn from the study.

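### Protocol Section 7.2 stops safety follow-up once a participant is classed lost to follow-up, so one so classed after Visit 2 is not tried at the D181 call for the 6-month SAE/AESI endpoint

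*Protocol*

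**What the plan says.** Protocol Section 3 (Table 3.1) sets the endpoint: "Presence of SAEs and AESIs, throughout the study period (up to 6-month follow-up"). The Schedule of Activities has one return visit (Visit 2, D31 with a 14-day window) and one later contact, the safety telephone call at D181 (+14 days). Section 8.3.2 makes that call the means of the 6-month follow-up.

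Section 7.2 treats early terminations in two ways. In general, "the site should attempt to contact them and complete all scheduled safety follow-ups, except if they specified that they do not want to be contacted". One group is exempted: "For participants where the reason for early termination is lost to follow-up, the site will not attempt to obtain further safety information".

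Section 7.3 defines that group: "A participant will be considered lost to follow-up if he or she repeatedly fails to return for scheduled visits and is unable to be contacted". After a missed visit, "The site must attempt to contact the participant and reschedule the missed visit as soon as possible". Before the status is given, the site must make every effort to regain contact: where possible 3 calls and, if necessary, a certified letter, or at least a determination of health status. A participant who stays unreachable is treated as withdrawn. No earliest date for this is set.

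On counting, SAP Section 5.3 defines the Safety Analysis Set (SafAS) as "Participants who have received the study vaccine", with no follow-up requirement. SAP Section 4.3.1.2.5 analyses SAEs in three periods: within 30 days, from D32 to the last participant contact, and "During the study (ie, all SAEs occurred during the study").

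**The concern.** Early termination normally leaves the 6-month safety call in place. The exception removes it for the participants about whom least is known. If contact fails around Visit 2, the call is ruled out some 150 days before it falls due (D31 to D181), although it is already scheduled for everyone and could be tried again.

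The trigger also fits the schedule poorly. Section 7.3 speaks of a participant who "repeatedly fails to return for scheduled visits and is unable to be contacted by the study site", but there is only one visit to return to. Sites are left to decide when the status applies.

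At stake is the completeness of SAE ascertainment, and a modest understatement of SAE percentages if unobserved participants remain in the denominator. If loss of contact is related to illness, the understatement would be larger, and it could not be checked because no attempt was made. The only AESI listed (Protocol Section 8.3.6) is anaphylaxis, so the practical concern is SAEs.

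**Working it through.** **Who is not called.** The provisions combine as follows.

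- Missed Visit 2, then reached: remains in the study and is due the D181 call.
- Early termination for another reason: scheduled safety follow-up is still attempted unless contact is refused (7.2).
- Missed Visit 2, unreachable after the 7.3 efforts, classed lost to follow-up: no further attempt (7.2), and nothing in 7.3 postpones that status to D181.

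Only the third group is affected. For them the diary card, which is collected at Visit 2, is not retrieved there either. The call would ask about any SAE or AESI not yet reported, so it could also recover earlier events.

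**How they enter the percentages.**

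- Solicited reactions: missing presence is a category, and participants without a non-missing value leave the analysis (SAP 4.3.1.1.3).
- Unsolicited AEs, which include SAEs (Protocol 10.3.1): an event needs at least a verbatim term and must not be Grade 0 (SAP 4.3.1.2.1). There is no missing-presence category.
- Percentages are of the SafAS (SAP 5.4.2), missing safety data are generally not replaced (SAP 5.5.1), and no person-time rule is given.

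It follows by inference that a lost participant with no report stays in the denominator and contributes no event.

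**Inputs for size.** About 150 per group and 15% drop-out (Protocol 9.2). The plan's own figure reproduces: 150 × 0.85 = 127.5, given as 128 in the PPAS. That 15% covers all reasons for loss from the PPAS, so it serves only as an upper bound. The lower value of 2% loss and the true SAE proportion of 2% are assumptions.

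**Reported proportion from D32 onward.** Let p be the true proportion and d the share lost before D32, with loss unrelated to SAE risk and nothing learned passively. Reported = p × (1 − d):

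| d | Reported when p = 2% |
|---|---|
| 2% | 2% × 0.98 = 1.96% |
| 5% | 2% × 0.95 = 1.90% |
| 10% | 2% × 0.90 = 1.80% |
| 15% | 2% × 0.85 = 1.70% |

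At the upper bound the shortfall is 0.30 percentage points, or 0.003 × 150 = 0.45 participants per group.

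**What the call could recover.** If a share r of those lost could be reached at D181, reported = p × (1 − d × (1 − r)). At d = 15%, r = 0 gives 1.70%, r = 0.5 gives 2% × 0.925 = 1.85%, and r = 1 gives 2.00%. The documents give no r.

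**Exact (Clopper-Pearson) limits.** With no events, the upper 95% limit is 2.43% on 150, against 2.48% on 147 followed (d = 2%) and 2.84% on 128 followed (d = 15%). With 3 events, 3/150 = 2.00% (0.41% to 5.73%), against 3/128 = 2.34% (0.49% to 6.70%).

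**The case against.** The strongest reply is that the rule is narrow and its effect small.

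- A reader might infer that anyone who misses Visit 2 is never called again. The documents do not support that. Section 7.3 requires contact and rescheduling first, and both non-return and failed contact before the status applies.
- Section 7.3 sets no deadline, and its contact steps also cover a participant who cannot be reached as the Schedule of Activities plans. A site could therefore leave the status open until D181. This stands as an ambiguity, but once the status is assigned the instruction in 7.2 is explicit.
- A reader might infer that the SAP declares lost participants event-free. It does not. Events reported before loss count, SAEs may be reported at any time during the study, and under Protocol 8.3.1 a related SAE learned of after discharge must be notified. These routes are passive, however, and do not replace a scheduled enquiry.
- A reader might take 15% × 150/180 = 12.5% of planned follow-up time as the cost of the sentence. That borrows all-cause drop-out as the loss rate and assumes that everyone lost would be reached at D181.
- The analyses are descriptive, arms are randomised, and no differential loss is shown. A shift of 0.45 participants per group is small beside an exact interval of 0.41% to 5.73%.
- A count of completed follow-up may already be planned. Disposition is to be summarised (SAP 5.4.1), an end-of-study status is collected (SAP 4.3.1.3.6), and the table shells are not in the text reviewed.

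These points limit the size of the concern. They do not explain why an already scheduled safety call should be withheld from vaccinated people who have not refused it.

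**Conclusion.** The point holds in limited form. A participant classed lost to follow-up after Visit 2 is not tried at the only later scheduled contact for the 6-month SAE/AESI endpoint, and the SAP does not say how that unobserved time enters the SAE percentages.

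The understatement is modest if loss is unrelated to illness: from 2% to between 1.96% and 1.70% over the assumed range of loss, of which the fix recovers only the part belonging to people reachable at D181. That loss is related to illness is plausible, but the documents do not establish it. This is a cheap improvement to safety ascertainment, and it does not invalidate the safety analysis.

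**What to change.** - **Protocol 7.2:** replace the exception. The scheduled D181 (+14 days) safety call is attempted for every vaccinated participant who has not refused further contact, including those earlier recorded as lost to follow-up.
- **Protocol 7.3:** assign final lost-to-follow-up status for the 6-month endpoint only after those attempts fail.
- **SAP 5.4.2:** report, per arm, the number of SafAS participants with a completed D181 contact beside the SAE and AESI percentages. This is useful even if the protocol is not amended.

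The cost is a short amendment, one SAP line and some extra call attempts, a number of which will fail. Under the same assumed range these would concern 0.02 × 750 = 15 to 0.15 × 750 = 112.5, about 113, participants across the trial. The upper figure overstates the number, because it counts every reason for drop-out.

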7.3 Lost to Follow-up

A participant will be considered lost to follow-up if he or she repeatedly fails to return for scheduled visits and is unable to be contacted by the study site.

The following actions must be taken if a participant fails to return to the site for a required study visit or cannot be contacted as planned in the SoA:

- The site must attempt to contact the participant and reschedule the missed visit as soon as possible and counsel the participant on the importance of maintaining the assigned visit schedule and ascertain whether or not the participant wishes to and/or should continue in the study.
- Before a participant is deemed lost to follow-up, the investigator or designee must make every effort to regain contact with the participant (where possible, 3 telephone calls and, if necessary, a certified letter to the participant's last known mailing address or local equivalent methods), or at least to determine his/her health status while fully respecting his/her rights. These contact attempts should be documented in the participant's medical record.
- Should the participant continue to be unreachable, he/she will be considered to have withdrawn from the study.

Discontinuation of specific sites or of the study as a whole are handled as part of [Appendix 10.1](#).

8 Study Assessments and Procedures

- Study procedures and their timing are summarized in the SoA. Protocol waivers or exemptions are not allowed.
- Immediate safety concerns should be discussed with the Sponsor immediately upon occurrence or awareness to determine if the participant should continue or discontinue study intervention.
- Adherence to the study design requirements, including those specified in the SoA, is essential and required for study conduct.
- All screening evaluations must be completed and reviewed to confirm that potential participants meet all eligibility criteria. The investigator will maintain a screening log to record details of all participants screened and to confirm eligibility or record reasons for screening failure, as applicable.

Blood samples will be collected as described in the SoA table ([Section 1.3](#)).

The maximum amount of blood collected from each participant over the duration of the study, including any extra assessments that may be required, will not exceed 40 mL. Repeat or unscheduled samples may be taken for safety reasons or for technical issues with the samples.

Guidance and information for the sample collection, preparation, storage, and shipment are provided in the Operating Guidelines.

[figure not shown]
8.1 Efficacy and Immunogenicity Assessments

8.1.1 Efficacy Assessments

No clinical efficacy data will be obtained in the study.

[figure not shown]
8.1.2 Immunogenicity Assessments

[figure not shown]
Multiplexed opsonophagocytic killing assay (MOPA)

This method will be performed on BL0001 and BL0002 collected on D01 and D31 respectively. Assays will be performed by PPD (a CRO laboratory), Richmond (VA), USA.

Pneumococcal capsular polysaccharide – electro-chemiluminescent assay (PnPS-ECL)

This method will be performed on BL0001 and BL0002 collected on D01 and D31 respectively. Assays will be performed by Sanofi Pasteur Global Clinical Immunology (GCI), Swiftwater (PA), USA.

8.2 Safety Assessments

This section presents safety assessments other than adverse events which are presented in [Section 8.3](#).

Planned time points for all safety assessments are provided in the SoA ([Section 1.3](#)).

8.2.1 Medical History

Prior to enrollment, participants will be assessed for pre-existing conditions and illnesses, both past and ongoing. Any such conditions will be documented in the source document. Significant (clinically relevant) medical history (reported as diagnosis) including conditions/illnesses for which the participant is or has been followed by a physician or conditions/illnesses that could resume during the course of the study or lead to an SAE or to a repetitive outpatient care will be collected in the CRF.

8.2.2 Physical Examinations

At Visit 1, the Investigator or a delegate will perform a physical examination based on medical history and including evaluation of the following body systems: general appearance, skin, head, eyes, ears, nose, throat, heart, lungs abdomen, musculoskeletal, extremities, neurological and lymph nodes examination. A targeted physical examination may also be performed at Visit 2, as necessary. Information will be recorded in the source document.

Temperature measurement will be done during the physical examination before vaccination and recorded in the source document.

8.2.3 Vital Signs

Axillary pre-vaccination temperature will be systematically collected by the investigator on the source document. Tympanic, skin, and temporal artery thermometers must not be used.

8.2.4 Clinical Safety Laboratory Assessments

Urine pregnancy testing will be performed in women of childbearing potential before vaccination.

8.3 Adverse Events and Serious Adverse Events

The definitions of an AE, SAE, and the different categories of AEs can be found in [Appendix 10.3](#).

AEs will be reported by the participants to the investigator, then by the investigator to the Sponsor.

The investigator and any qualified designees are responsible for detecting, documenting, and recording events that meet the definition of an AE or SAE and remain responsible for following up AEs that are serious, considered related to the study intervention or study procedures, or that caused the participant to discontinue the study (see [Section 7](#)).

8.3.1 Time Period and Frequency for Collecting AE and SAE Information

Immediate Post-vaccination Observation Period

Participants will be kept under observation for 30 minutes after vaccination to ensure their safety. The post-vaccination observation should be documented in the source document and immediate events will be recorded at D01 in the eCRF.

Reactogenicity

Solicited injection site reactions will be collected from D01 to D08 after vaccination.

Solicited systemic reactions will be collected from D01 to D08 after vaccination.

The solicited injection site reactions and systemic reactions that are pre-listed in the diary cards and CRF, together with the intensity scales, are presented in [Appendix 10.3.5.1.1](#).

Unsolicited Non-serious Adverse Events

Unsolicited non-serious adverse events will be collected from D01 to D31 after vaccination.

The intensity grading scale for unsolicited non-serious adverse events is presented in [Appendix 10.3.5.1.2](#).

Adverse Events of Special Interest (AESIs)

AESIs will be collected throughout the study period, from D01 until 6 months after vaccination.

See [Section 8.3.6](#) for the list of AESIs.

SAEs

Information on SAEs will be collected and assessed throughout the study, from D01 until 6 months after vaccination.

Medical occurrences that begin before the start of study intervention but after obtaining informed consent will not be recorded on the AE section of the CRF.

All SAEs will be recorded and reported to the Sponsor or designee immediately and under no circumstance should this exceed 24 hours, as indicated in [Appendix 10.3](#). The investigator will submit any updated SAE data to the Sponsor within 24 hours of it being available.

Investigators are not obligated to actively seek AE or SAE after conclusion of the study participation. However, if the investigator learns of any SAE, including a death, at any time after a participant has been discharged from the study, and he/she considers the event to be reasonably related to the study intervention or study participation, the investigator must promptly notify the Sponsor.

